1.0 Objectives*

The primary objective of this protocol is to **conduct an open pilot to elicit initial quantitative and qualitative feedback on the intervention that we are developing**. To do so, we will deliver our novel intervention to 2 consecutive groups of female colorectal and anal cancer survivors ($n \sim 10$ per group, total $N \sim 20$). Participants will provide feedback regarding intervention acceptability, feasibility, and perceived benefit.

To inform plans for ongoing program refinement, we will also elicit specific feedback regarding study assessment tools, recruitment procedures, and group composition.

In future, larger-scale, work, we intend to conduct a larger randomized pilot trial to assess intervention acceptability, feasibility, as well as preliminary efficacy on essential indices of sexual well-being.

2.0 Background*

Many female colorectal and anal cancer survivors experience poor sexual quality of life. Over 700,000 American women are living with gastrointestinal (GI) malignancies, including colorectal or anal cancer.¹⁻³ Mortality for these gastrointestinal cancers is also decreasing, suggesting that many women will live as cancer survivors for many years.¹ As a result of GI cancer treatments such as surgery, radiation, and chemotherapy, many survivors experience serious long-term side effects such as infertility, diarrhea, incontinence, sexual dysfunction, and in many cases, the need for a temporary or permanent stoma and colostomy bag.^{4,5} Specific sexual effects commonly experienced by female survivors include vaginal dryness and dyspareunia (reported by roughly 30% of colorectal cancer survivors).^{4,6} Further, these physical changes yield indirect effects on psychological and relational factors as body image, libido, and ability to enjoy intimacy.^{6,7}

Unfortunately, women's sexual well-being is often neglected in survivorship care.⁸⁻¹⁰ Nurse-delivered patient education about vaginal dilators, moisturizers, and lubricants demonstrates initial promise for vaginal stenosis among colorectal and anal cancer survivors,^{11,12} but does not address other aspects of sexual well-being, such as body image, reduction of physiological stress symptoms, and communication. Thus, there is a need for a novel mind-body intervention to target interacting physiological, emotional, cognitive, and relational contributors to women's sexual well-being in colorectal and anal cancer survivorship.

Based on the established scientific literature as well as our own preliminary qualitative research, we anticipate that our novel group-based intervention holds promise for women who experience these common and distressing, yet under-addressed symptoms and

PROTOCOL TITLE: Open Pilot Trial of a Mind-Body Sexual Well-Being Program

propose to conduct an initial open pilot trial of our intervention to elicit feedback for future refinement efforts.

3.0 Inclusion and Exclusion Criteria*

3.1 Screening

The study team will utilize the EHR (Epic) to screen potentially eligible survivors, as we have done for existing clinical and research programs. A clinical research coordinator (CRC) will review survivors' EHR to ensure they meet the study eligibility criteria, with consultation from a study investigator or medical provider as necessary.

3.2 Inclusion/Exclusion

Inclusion Criteria

1. Female sex
2. English-speaking
3. Aged 18 or older
4. Receive any cancer care at MGH-CC sites (Boston, Waltham, Danvers, Newton Wellesley Hospital)
5. Completed initial active treatment (i.e., surgery, radiation, chemotherapy) for colorectal or anal cancer approximately 3 months or more prior to enrollment or diagnosed longer than 3 months ago if in metastatic cancer treatment.

Consistent with the National Comprehensive Cancer Network survivorship guidelines¹³ and screening procedures previously implemented by our team (DF-HCC Protocol #22-586), we will include female survivors of all ages endorsing sexual health concerns that negatively impact quality of life. Women on long-term endocrine therapies will not be excluded.

Given the scientific aims of this study (i.e., addressing women's sexual well-being), we are including only participants who identify their sex at birth as female and/or current gender identity as woman. Individuals who identify with all races and ethnic groups are eligible for this trial.

Exclusion Criteria

1. Active psychiatric or cognitive comorbidity that prohibits the capacity to provide informed consent as determined by the study PI, a licensed psychologist, in collaboration with the patient's medical team
2. Adults unable to complete study procedures in English.
3. Adults who participated in the qualitative phase of this trial are not eligible for the pilot groups.

PROTOCOL TITLE: Open Pilot Trial of a Mind-Body Sexual Well-Being Program

We are unfortunately unable to include individuals who are not fluent in English for this small open pilot trial, as the intervention content is currently only available in English (which is also the primary language in which our small study team is qualified to provide clinical services). We intend to prioritize broader inclusion of individuals who speak other languages in future larger-scale work.

1.1 Special Populations:

We will not enroll the following special populations: adults unable to consent, individuals who are not yet adults (i.e., < age 18), pregnant women, and prisoners.

4.0 Study-Wide Number of Subjects*

We will enroll up to 20 individuals, all recruited from MGH main campus and satellite sites, in this study.

5.0 Study-Wide Recruitment Methods*

N/A – this is a single site study.

6.0 Multi-Site Research*

N/A – this is a single site study.

7.0 Study Timelines*

We anticipate that participants will have approximately 4 months of active involvement. During this time, they will complete 6 approximately 1.5 hour approximately weekly group sessions as well as provide survey data and exit interviews.

8.0 Study Endpoints*

Primary aim:

We will conduct a single-arm feasibility trial to examine the feasibility and acceptability of delivering a group-based mind-body sexual well-being intervention delivered via videoconference technology for up to 20 women who have completed treatment for colorectal or anal cancer. Specifically, we will assess whether a virtually-delivered, 6-week sexual well-being group intervention for female colorectal and anal cancer survivors is: **a) Feasible** (assessed by evaluating recruitment/enrollment rates and adherence to sessions) and **b) Well-accepted** (defined by program satisfaction, ease and utility). Given the preliminary, open pilot nature of this protocol, we will not set *a priori* criteria to establish feasibility and efficacy but will rather interpret each of these metrics holistically. Qualitative feedback gathered in post-intervention exit interviews will also add to our understanding of feasibility and acceptability (see Table 1 below).

Secondary aim:

PROTOCOL TITLE: Open Pilot Trial of a Mind-Body Sexual Well-Being Program

We will explore the preliminary effects of the intervention on psychosocial measures of satisfaction with sex life and impact of functional limitations, coping abilities, acceptance of body image changes, loneliness, and anticipated stigma (see Table 1). As noted above, we will not set *a priori* criteria to establish preliminary efficacy, nor will we consider statistical significance as an indicator of study efficacy. Instead, we will consider pre-post intervention effect sizes to consider the need for refinement of study procedures/measurement in a future efficacy trial.

We will complete the open pilot trial after completing 2 group intervention cohorts with approximately 10 participants per group. Primary outcomes of interest are listed below:

Table 1. Measures for Open Pilot Data Collection		
Construct	Measurement	Data Source
Feasibility		
Recruitment	Percent screened of eligible patients identified	Clinic logs (Epic) and recruitment tracking
Screening/Eligibility	Percent eligible of individuals screened	Recruitment tracking log
Enrollment	Percent randomized of those eligible	Recruitment tracking & randomization log
Engagement	(*) Percent completed 66% (4/6 sessions) of those enrolled	Session attendance logs
Data Collection	Percent with complete pre-post and post-session data	REDCap tracker
Acceptability		

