Cognitive-Behavioral Acceptance of Body Changes	Modified FACT/McGill Body Image Scale (FACT-MBIS)- Self-Image subscale ¹⁹	Self-report in REDCap (11 items)
Anticipated Stigma	Modified chronic Illness Anticipated Stigma Scale- Healthcare workers subscale ²⁰	4 items - REDCap
Self-efficacy regarding sexual well-being	Single item-questions created for this study regarding understanding of: 1) cancer impact on sexual health; 2) communication strategies for sexual well-being; 3) use of relaxation strategies for sexual well-being; 4) impact of thoughts and feelings on sexual well-being; 5) how to access appropriate resources for sexual well-being	5 items - REDCap

* Indicates primary measure of acceptability or feasibility; ^ Indicates primary effect size of interest

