6. Meaning-Making of Change	Personal values and goals for sexuality/intimacy; relapse prevention	1. Personal values and meaning-making of change; 2. Review of goals for the future; 3. Use of art/creativity as a coping resource

We will enroll approximately 10 women per group into 2 groups (total $N \sim 20$), based on logistic considerations and previous success with survivorship groups of a similar size.

We will run groups consecutively so that any necessary changes from the first open pilot group may be incorporated and re-examined in the second. Based on participant feedback gathered in our qualitative study, we expect that groups will meet online via Zoom.

Groups will be led by study PI **[name]**, who has expertise in mind-body targets of illness adjustment, in collaboration with Co-I **[name]**, who will lend expertise in medical aspects of sexuality in GI cancer survivorship. We expect that each of the 6 weekly sessions will last for approximately 90 minutes and include content related to mind-body medicine and complementary medical resources (e.g., dilators, lubricants, and moisturizers) relevant to survivors' sexual well-being. The rationale for this treatment structure is based on our current survivorship resiliency groups, other cognitive behavioral sexual health interventions for cancer survivors and an existing brief nursing intervention for sexual health in GI oncology led by [name]. During the open pilot, **[name]** will provide clinical supervision of **Drs. [name] and [name]** and perform fidelity ratings of audio-recorded intervention sessions using checklists developed for the study. **Drs. [name] and [name]** will also be available for clinical consultation.

Participants will complete electronic informed consent prior to initiation of study procedures. To inform ongoing intervention refinement, we will ask participants to complete 15-minute survey batteries via REDCap at baseline and after the 6-session program, including assessments of intervention feasibility and acceptability as well as psychosocial outcomes including contentment with sex life, psychosocial impact of functional limitations, coping abilities, acceptance of body image changes, loneliness, and anticipated stigma (see Table 1 above). Measures have been selected for their

demonstrated strong psychometric properties in cancer populations, sensitivity to change, and brevity.

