11.2 Sample size justification

Following guidelines for pilot studies and exploratory mixed methods research, we have based sample size for this small proof-of-concept study ($N = 2$ groups with $n \sim 10$ patients/group) on pragmatics and previous pilot research by our group^{21, 23} suggesting that this sample size will be sufficient to inform initial protocol refinement.

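### Pre-post effect sizes alone cannot show which measures need refining; a per-scale performance table would help and costs little

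*Combined protocol and SAP*

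**What the plan says.** The secondary aim in section 8.0 explores change in six constructs: "satisfaction with sex life and impact of functional limitations, coping abilities, acceptance of body image changes, loneliness, and anticipated stigma". It sets no a priori criteria and does not treat statistical significance as evidence of efficacy. In their place, "we will consider pre-post intervention effect sizes to consider the need for refinement of study procedures/measurement in a future efficacy trial". It gives no rule or interval, and it does not say that scales will be ranked.

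Section 11.1 labels the effect sizes exploratory and specifies them for one outcome only, Positive Satisfaction with Sexuality. Table 1 marks the same outcome as the primary effect size of interest.

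Other information on measurement is planned. Section 1.0 says "we will also elicit specific feedback regarding study assessment tools, recruitment procedures, and group composition". Table 1 has a 1-5 rating of how easy the surveys were to complete, exit-interview comments on the surveys, and a percentage of participants with complete data.

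Section 9.0 says that the measures were chosen for their "demonstrated strong psychometric properties in cancer populations, sensitivity to change, and brevity". Table 1, however, labels the body-image and anticipated-stigma scales as modified, and its five self-efficacy items are "Single item-questions created for this study regarding understanding of" sexual well-being topics.

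The design is single-arm, with at most 20 women (sections 4.0 and 8.0).

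**The concern.** The product of this pilot is a refined protocol for a randomized pilot, so the evidence used to judge the measures matters. A small pre-post change has several possible causes. Most women may already sit at the floor or ceiling at baseline. Items may be skipped, which sections 14.0 and 24.0 expressly allow. The scale may be unreliable in its modified form. Or the program may do little on that domain. The first three point to changing the measure and the last to changing the program. The effect size has the same appearance in every case, and the plan has no per-scale summary that would separate them. A serviceable measure could be replaced, or a poorly working one carried forward, because of a number that does not bear on the question.

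**Working it through.** **Inputs from the documents.** n is up to 20 (section 4.0), in one arm with two time points (sections 8.0 and 11.1). Six constructs are named in 8.0, and one effect-size analysis is specified in 11.1. The sample size was based "on pragmatics and previous pilot research by our group" (section 11.2). No power, precision, SD or effect size is stated, so there is no figure of the plan's own to reproduce.

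**Assumptions, not in the documents.** True standardized mean change d = 0.3 unless stated; correlation of change scores between scales (rho) 0, 0.3 or 0.5; 16 completers as a variant (20% loss); reliabilities of 0.8 and 0.5.

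**1. Can the effect size separate a weak measure from a weak program?** With d the mean change divided by the SD of change, unreliability shrinks it to d_obs = d_true × √reliability.
- d_true = 0.5, reliability 0.8: 0.5 × 0.894 = 0.45.
- d_true = 0.5, reliability 0.5: 0.5 × 0.707 = 0.35.

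A program with a true change of 0.35 on a perfectly reliable scale also gives 0.35. The two cases have the same expected value, so no sample size separates them on this statistic alone. The limit comes from the statistic and the single-arm design, not only from n.

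**2. How precise is one effect size?** SE ≈ √(1/n + d²/(2n)).
- n = 20, d = 0.3: √(0.05 + 0.00225) = 0.23. Simulation gives 0.24.
- n = 20, observed 0.4: exact 95% CI (noncentral t) −0.06 to 0.85.
- n = 16, observed 0.4: −0.12 to 0.90.

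The shifts in step 1 (0.05 to 0.15) are smaller than one SE. With a true change of 0.3 and n = 20, the observed value falls below 0.1 in about 18% of simulated trials. So the problem applies to the one scale in 11.1 without any comparison between scales.

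**3. How far apart can scales lie by chance?** Simulation with 20,000 trials, six scales, all true changes set equal at 0.3. Mean of highest minus lowest observed value:

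| n | rho 0 | rho 0.3 | rho 0.5 |
|---|---|---|---|
| 20 | 0.61 | 0.52 | 0.44 |
| 16 | 0.70 | 0.59 | 0.50 |

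Equal true effects are built in, so all of this spread is chance by construction. The table shows what chance can produce, not what share of the spread in this trial would be chance.

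**4. What share might be chance?** Share = chance variance / (chance variance + tau²), where tau is the SD of true effects between scales. With n = 20, d = 0.4 and six scales, the chance SD is 0.21 at rho 0.3 and 0.18 at rho 0.5.
- tau = 0.1: 82% and 77%.
- tau = 0.2: 53% and 45%.
- tau = 0.3: 33% and 27%.

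The share passes below one half when tau exceeds the chance SD, about 0.18 to 0.21 at these correlations. The documents give neither tau nor rho.

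**5. What would the planned information show?** The ease rating is one item for the whole survey, and completeness is one percentage for the data collection. Neither identifies a particular scale. Interview comments may do so, but only where participants raise it.

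**The case against.** The strongest reply is that 8.0 makes a modest statement. It says that effect sizes will be considered; it does not say that they will decide anything, and there is no rule for keeping or dropping a scale. Effect sizes are already called exploratory and significance is set aside. A reader might infer that the effect size is the only quantitative input on measurement. The ease rating and the completeness percentage in Table 1 contradict that. A reader might also infer that scales will be ranked by effect size and that the differences would be mostly chance. No ranking is planned, 11.1 specifies one scale, and the chance share depends on two quantities that the documents do not give. The sessions in Table 2 address different targets, so equal true effects are not an obvious default. All of this stands and limits the point.

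A further reply is that the replacement is noisy too: 3 of 20 women at the ceiling has an exact 95% CI of about 3% to 38%. That also stands. But a floor, ceiling or skip percentage at least addresses how the scale works, whereas an effect size does not, however precise it is.

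How well the two modified scales perform cannot be judged from these documents. The point is only that the general statement in 9.0 does not settle it for modified scales and new items.

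**Conclusion.** The point holds in a limited form. The statistic that 8.0 names for considering measurement refinement cannot, on its own, distinguish a poorly working scale from a program with little effect, and a larger single-arm sample would not change that. At about 20 women it is also imprecise: sampling SD about 0.24 for an assumed true change of 0.3, with chance gaps of about 0.4 to 0.6 across six scales if true effects are equal and change scores correlate between 0.5 and 0. The planned feedback fills part of the gap but, in its numerical form, not scale by scale. The documents do not support saying that scales will be chosen on effect size or that differences between them will be mostly noise. No efficacy claim depends on this, so severity is low and the change is a cheap improvement.

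**What to change.** In sections 8.0 and 11.1:
- Report pre-post effect sizes descriptively, each with a confidence interval, and state that no scale will be kept or changed on effect size alone.
- Add one table covering each Table 1 outcome scale at T0 and T1: percent of women at the floor and at the ceiling, percent of items skipped and, for multi-item scales, internal consistency. Read it with the ease rating and interview feedback already planned.
- Reconcile the scope: 8.0 names six constructs and 11.1 specifies an effect size for one. State which scales will have effect sizes.

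The cost is a short rewording and one descriptive table from item data already collected in REDCap, with no added burden on participants. The downside is slightly more analysis work and summaries that are themselves imprecise at this sample size, internal consistency included. They should guide judgment together with the interviews and not act as cut-offs.

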Cognitive-Behavioral Acceptance of Body Changes	Modified FACT/McGill Body Image Scale (FACT-MBIS)- Self-Image subscale ¹⁹	Self-report in REDCap (11 items)
Anticipated Stigma	Modified chronic Illness Anticipated Stigma Scale- Healthcare workers subscale ²⁰	4 items - REDCap
Self-efficacy regarding sexual well-being	Single item-questions created for this study regarding understanding of: 1) cancer impact on sexual health; 2) communication strategies for sexual well-being; 3) use of relaxation strategies for sexual well-being; 4) impact of thoughts and feelings on sexual well-being; 5) how to access appropriate resources for sexual well-being	5 items - REDCap

* Indicates primary measure of acceptability or feasibility; ^ Indicates primary effect size of interest

9.0 Procedures Involved*

This is an open pilot trial to gather initial data regarding feasibility, acceptability, and perceived impact of a 6-session mind-body group intervention that we are developing to enhance sexual well-being among post-treatment female colorectal and anal cancer survivors. *Results of this open pilot will directly inform refinement of our study protocol, for ongoing testing in a future larger randomized pilot trial.* A brief outline of the content that may be included in this intervention is below:

Table 2. Overview of Anticipated Intervention Structure		
Topic Discussed	Sexual Well-Being Target	Session Content
1. Defining Stress and Sexual Sequelae of Treatment	Uncertainty about "normal" changes following treatment; education about stress-sexuality connection	1. Session ground rules and what to expect; 2. Effects of cancer treatment on sexual function; 3. Stress reactivity and relaxation response.
2. Social Factors & Women's Sexual Well-Being in Context	Stigma and shame; difficulties communicating needs to medical providers and partners	1. Social and cultural factors that influence women's sexuality; 2. Skills for assertive communication; 3. Overview of medical resources for sexual health (e.g., dilators, lubricants, moisturizers) and common barriers to use

PROTOCOL TITLE: Open Pilot Trial of a Mind-Body Sexual Well-Being Program

3. Awareness of Thoughts and Feelings	Unhelpful stress-related thoughts about sexuality that interfere with libido and health behaviors	1. Mindful, nonjudgmental awareness of thoughts and feelings related to sexuality; 2. CBT strategies to challenge unhelpful thoughts; 3. Mindfulness as a resource to cultivate awareness of body sensations
4. Body Image Changes	Body image post-treatment and strategies to manage use of ostomy bag (if applicable)	1. Self-compassion & body acceptance; 2. Barriers to (and facilitators of) health behavior engagement; 3. Introduction of guided imagery to cultivate pleasant experience
5. Meditative Movement	Pain/tightness and changes to physical sensation; reactivity to physical sensation	1. Interoceptive awareness of body sensations; 2. Review of strategies for mindful non-judgment; 3. Gentle yoga/movement as a coping resource; 4) Behavioral activation and planning for pleasant physical sensations
6. Meaning-Making of Change	Personal values and goals for sexuality/intimacy; relapse prevention	1. Personal values and meaning-making of change; 2. Review of goals for the future; 3. Use of art/creativity as a coping resource

We will enroll approximately 10 women per group into 2 groups (total $N \sim 20$), based on logistic considerations and previous success with survivorship groups of a similar size.

We will run groups consecutively so that any necessary changes from the first open pilot group may be incorporated and re-examined in the second. Based on participant feedback gathered in our qualitative study, we expect that groups will meet online via Zoom.

Groups will be led by study PI **[name]**, who has expertise in mind-body targets of illness adjustment, in collaboration with Co-I **[name]**, who will lend expertise in medical aspects of sexuality in GI cancer survivorship. We expect that each of the 6 weekly sessions will last for approximately 90 minutes and include content related to mind-body medicine and complementary medical resources (e.g., dilators, lubricants, and moisturizers) relevant to survivors' sexual well-being. The rationale for this treatment structure is based on our current survivorship resiliency groups, other cognitive behavioral sexual health interventions for cancer survivors and an existing brief nursing intervention for sexual health in GI oncology led by [name]. During the open pilot, **[name]** will provide clinical supervision of **Drs. [name] and [name]** and perform fidelity ratings of audio-recorded intervention sessions using checklists developed for the study. **Drs. [name] and [name]** will also be available for clinical consultation.

Participants will complete electronic informed consent prior to initiation of study procedures. To inform ongoing intervention refinement, we will ask participants to complete 15-minute survey batteries via REDCap at baseline and after the 6-session program, including assessments of intervention feasibility and acceptability as well as psychosocial outcomes including contentment with sex life, psychosocial impact of functional limitations, coping abilities, acceptance of body image changes, loneliness, and anticipated stigma (see Table 1 above). Measures have been selected for their

demonstrated strong psychometric properties in cancer populations, sensitivity to change, and brevity.

Participants will also be invited to complete a brief qualitative exit interview with a member of our study team, regarding perceived benefit of the intervention as well as and strengths and weaknesses of program content and delivery format to inform ongoing intervention refinement (see script attached to this protocol). Participants will be offered up to \$60 for participation in study assessments (\$20 each for pre- and post- assessments as well as the qualitative exit interview).

At the end of each session, the interventionist will complete an electronic process form indicating the length, location, and content of the session. We will also tally total number and timing of sessions attended for each participant. Attendance data will be logged in REDCap by a CRC.

